10.2.5. Subgroup Analyses

The effectiveness analyses will be evaluated in each of the following subgroups: Women, Men, Reduced Ejection Fraction (< 40%), Preserved Ejection Fraction ($\geq 40\%$), Ischemic Etiology, Non-ischemic Etiology, With ICD/CRT-D, and Without ICD/CRT-D.

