12.2. Sample Size Considerations

Effectiveness Sample Size Determination

For the primary effectiveness endpoint of HF hospitalization rate during 1 year, 300 patients will provide greater than 90% power to meet the efficacy goal (upper confidence limit less than the HF hospitalization rate in the year prior to enrollment), using a one-sample, two-sided Poisson confidence interval with alpha of 0.05.

Safety Sample Size Determinations

For the two-year primary safety endpoint of freedom from device-related complications, using an exact two-sided test for one-sample binomial proportions with alpha of 0.05, a sample size of 619 subjects will provide greater than 90% power to detect a difference as small as 5% from the null proportion rate of 0.80 (i.e., objective performance criterion of 80%). For sensor failures at 2 years, a sample size of 663 subjects provides greater than 90% power to detect a difference as small as 3.5% from the null proportion rate of 0.90 (i.e., objective performance criterion of 90%).

This confidential document is the property of Abbott and shall not be reproduced, distributed, disclosed or used without the express written consent of Abbott

Clinical Investigation Plan

Thus, the sample size for this study is driven by the safety endpoints. The 2 year attrition rate in CHAMPION was 49.1% (228/550). To ensure sufficient patients are enrolled to adequately evaluate safety and efficacy, 1200 subjects will be enrolled.

Note that at least 35% of the 1200 enrolled patients (420) must be women resulting in approximately 206 women completing the trial (assuming a 49% attrition rate). This sample size will provide greater than 90% power to meet the goal for effectiveness. Regarding freedom from device-related complications and freedom from sensor failures, 206 women will provide greater than 90% power to detect a difference as small as 0.06 from the null proportion rate of 0.90.

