12.6. Safety Analyses

The safety analyses will be performed using the Safety Population. The data will be summarized using univariate statistics (e.g., N, mean, standard deviation, median, minimum and maximum) or frequency (e.g., N, %) as appropriate.

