12.7.2. Supplemental Analyses

Mortality

The mortality rate over 1 year in study will be reported. Plotting and analysis of survival data will be displayed using Kaplan-Meier methods.

HF Hospitalization or Death

The annualized HF hospitalization or death rate parameter, λ , at 1 year will be compared to the HF hospitalization rate in the year prior to enrollment using a two-sample, two-sided Poisson confidence interval. If the two-sided, upper 95% confidence interval for the PAS rate parameter is less than that in the year prior to enrollment, then the hypothesis will be met.

Mathematically stated, the hypothesis is:

$$H_0: \lambda_{(12 \text{ month HF Hospitalization or Death Rate})} \geq \lambda_{(\text{HF hospitalization rate in year prior to enrollment})}$$

$$H_a: \lambda_{(12 \text{ month HF Hospitalization or Death Rate})} < \lambda_{(\text{HF hospitalization rate in year prior to enrollment})}$$

where $\lambda_{(12 \text{ month HF Hospitalization or Death Rate})}$ = the HF hospitalization or death rate parameter at 1 year in the PAS and $\lambda_{(\text{HF hospitalization rate in year prior to enrollment})}$ = the HF hospitalization rate in the year prior to enrollment.

Patient Compliance

Patient device usage over the course of the trial will be examined. The total number of PA pressure readings taken will be reported as a percentage of patient days at home.

This confidential document is the property of Abbott and shall not be reproduced, distributed, disclosed or used without the express written consent of Abbott

Clinical Investigation Plan

Training Evaluation

To assess the effectiveness of the training program, the safety and effectiveness results will be reported for:

- 1) Academic Hospitals
- 2) Community Hospitals

Subgroup Analyses

The effectiveness analyses will be evaluated in each of the following subgroups:

- 1) Women
- 2) Men
- 3) Reduced Ejection Fraction (< 40%)
- 4) Preserved Ejection Fraction ($\geq 40\%$)
- 5) Ischemic Etiology
- 6) Non-ischemic Etiology
- 7) With ICD/CRT-D
- 8) Without ICD/CRT-D

Quality of Life Evaluations

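### Section 12.2 states over 90% power for both safety endpoints in women, but no safety analysis in women is prespecified

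*Combined protocol and SAP*

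**What the plan says.** Section 12.2 sets the quota and the expected number of completers: "Note that at least 35% of the 1200 enrolled patients (420) must be women resulting in approximately 206 women completing the trial". It first claims over 90% power for effectiveness in these women, then turns to safety: "Regarding freedom from device-related complications and freedom from sensor failures, 206 women will provide greater than 90% power to detect a difference". The effect size is a "difference as small as 0.06 from the null proportion rate of 0.90", applied to both safety endpoints.

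The analysis sections read as follows.

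- **12.6 and 12.6.1.** "The safety analyses will be performed using the Safety Population". The two hypotheses (above 80% for complications, above 90% for sensor failure) and the two-step hierarchy concern the whole cohort. Nothing is stated by sex.
- **10.2.5.** "The effectiveness analyses will be evaluated in each of the following subgroups: Women, Men", followed by the other subgroups. Section 12.7.2 has the same list with the same opening, "The effectiveness analyses will be evaluated in each of the following subgroups". The main synopsis, the sub-study synopsis and 13.5.5 also tie Women and Men to effectiveness.
- **Training evaluation (12.7.2, 13.5.5 and both synopses).** This is the one place where safety results are split, by academic and community hospital.
- **Appendix L.** The demographic table has male and female columns. The tables for complications and sensor failures, mortality and serious adverse events do not.

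**The concern.** A sample size, a difference, a null value and a power together describe a particular test. For effectiveness in women, a matching analysis is listed in 12.7.2. For safety in women, none is. If the plan is followed exactly, the study enrols at least 420 women, states what they can show about safety, and reports no complication or sensor-failure result for them.

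The whole-cohort result cannot stand in for it. With 35% women, about two thirds of subjects may be men, and a favourable rate in men can carry the pooled proportion over the criterion when the rate in women does not exceed it. An analysis by sex added later would also be weaker than a prespecified one, because the study is open-label and reports safety results every six months for its first two years.

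**Working it through.** **Inputs from the documents.** 420 women out of 1200; 206 women completing; null 0.90 and difference 0.06 for women; criteria of 0.80 (complications) and 0.90 (sensor failure); exact one-sample binomial test, two-sided alpha 0.05; whole-cohort sizes 619 (0.80 against 0.85) and 663 (0.90 against 0.935); attrition 49.1%.

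**Assumption.** The exact test is stated for the whole cohort. I take it to apply to women too.

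**Step 1: reproduce the plan's figures.** Let c be the smallest count of event-free subjects with P(X ≥ c | n, p0) ≤ 0.025. Power is P(X ≥ c | n, p1).

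| n | p0 | p1 | c | Exact upper-tail alpha | Exact power |
|---|---|---|---|---|---|
| 619 | 0.80 | 0.85 | 515 | 0.0244 | 90.4% |
| 663 | 0.90 | 0.935 | 612 | 0.0245 | 90.5% |
| 206 | 0.90 | 0.96 | 194 | 0.0238 | 92.8% |

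The method recovers both whole-cohort statements and the one for women. As a calculation against 0.90, the 12.2 figure is right.

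**Step 2: what 206 women give against the plan's own complication criterion.** With p0 = 0.80, c = 177 (alpha 0.0177).

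- At the same difference, p1 = 0.86: power 56.2%.
- At p1 = 0.88: power 84.7%.
- At p1 = 0.886: power 90.3%, so about 90% power needs a difference near 0.086.

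The 12.2 sentence therefore describes a sensor-failure analysis in women, but not a complications analysis against 80%.

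**Step 3: can a pooled pass stand in?** Take 1200 × (1 − 0.491) = 610.8, or 611 evaluable. Split them 35/65: 214 women and 397 men. This uses 214 because 420 × 0.51 = 214.2; the plan's 206 equals 420 × 0.49. For n = 611 the pooled test passes at 565 or more event-free subjects (criterion 0.90) or 509 or more (criterion 0.80). Put women exactly at the criterion and vary men. The pass probability is the upper tail of the sum of the two binomials.

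| Endpoint | Women | Men | Pooled test passes |
|---|---|---|---|
| Sensor failure | 90% | 93.5% | 47% |
| Sensor failure | 90% | 95% | 80% |
| Sensor failure | 90% | 96% | 94% |
| Complications | 80% | 85% | 51% |
| Complications | 80% | 87% | 82% |
| Complications | 80% | 90% | 99% |

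The first row for each endpoint gives men the plan's own whole-cohort design alternative. The higher rates are assumptions made to show the range.

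**The case against.** The strongest reply is that 12.2 is a sample-size note. It describes what 206 women could detect and does not promise a formal test. A reader might infer that the analysis will never be done, or that its power is zero. The documents do not support that: an unspecified test has undefined power, and the sponsor may still run the analysis. What stands is that nothing prespecifies it.

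A reader might also infer that the quota of women serves no purpose. It does serve one: effectiveness in women is a listed subgroup with its own power claim in the preceding sentence of 12.2.

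The opening line of 12.6 is weak evidence taken alone. It names an analysis set and does not bar summaries by sex. Section 12.1 makes a parallel statement for effectiveness, where subgroups are planned. The case rests on every sex-specific list being confined to effectiveness, while a safety split by hospital type is written out.

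Nothing in the documents suggests that women do worse on either endpoint, and the masking figures depend on the rate assumed in men. At the plan's own design alternatives the pooled test passes only about half the time, so the 94% and 99% figures are the upper end and not the expected case. Finally, Appendix L is a template for interim updates, so its missing columns do not settle the content of the final report.

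These replies limit the wording and the weight of the point. They do not supply the missing analysis.

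**Conclusion.** The point holds as an omission. Section 12.2 states over 90% power for two safety endpoints in women, and no safety estimate or test in women is prespecified. The primary hypotheses, the hierarchy, the error rate and the pass rule are unaffected, so this is an inexpensive repair that should be made and not a threat to the main result.

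A pooled pass does not show that women meet the criteria. With women exactly at the criterion it occurs about 47% to 94% of the time for sensor failure and 51% to 99% for complications, assuming 611 evaluable subjects, a 35% share of women and the stated rates in men.

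A reader might infer that adding the analysis would make the 12.2 statement true as written. It would for sensor failure (92.8%). For complications against the plan's 80% criterion, power at a 0.06 difference is 56.2%, so the sentence needs changing as well.

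**What to change.** 1. In 12.6.1, add a supplemental analysis along these lines: both 24-month safety endpoints will be estimated separately in women and in men by the primary method, with two-sided 95% confidence intervals shown against 80% for complications and 90% for sensor failure; these estimates lie outside the hierarchical test.
2. Add Male and Female columns to the Appendix L safety table, as the demographic table already has.
3. Amend the women's safety sentence in 12.2 so that each endpoint has its own criterion: for 206 women, 92.8% power for sensor failure (0.96 against 0.90); for complications, 56.2% at 0.86 against 0.80, with about 90% reached near 0.886.
4. If no safety analysis in women is intended, delete that sentence instead.

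The cost is plan wording and two table columns, with no new data and no more patients. The drawback is that intervals by sex will be wider than those for the whole cohort, and the results remain supplemental.

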Safety Measures:	
Primary safety endpoints will be evaluated at 2 years: 1) freedom from device/system related complications and 2) freedom from pressure sensor failure.
 
Safety will also be assessed throughout the study by the frequency of Adverse Device Effects (ADEs), Serious Adverse Events (SAEs) and Serious Adverse Device Effects (SADEs). A Clinical Events Committee (CEC) will evaluate all SAEs to determine whether or not the SAE is device / system-related complication or pressure sensor failure.

Effectiveness Measures:	
The primary effectiveness endpoint is the annualized HF hospitalization rate at 1 year
 
Supplemental analyses include mortality at 1 year, HF hospitalization or death at 1 year, patient compliance over the trial, training evaluation, Quality of Life evaluations, and subgroup analyses.
 
Information regarding all hospitalizations and deaths will be collected throughout the study and will be adjudicated by the CEC.

PAS Sub-study:	Sub-study within the main PAS cohort with an effectiveness endpoint of comparison of the HF hospitalization rate over 1 year in study to the 1 year HF hospitalization rate in Part 1 of the CHAMPION trial Control Cohort. The safety endpoints will be the same as the main PAS cohort.
Statistical Considerations:	
Primary Safety Endpoints
 
The primary safety hypotheses are that the device / system-related complication-free proportion of subjects will be at least 80% at 24 months (OPC used in the CHAMPION trial) and that the pressure sensor failure-free proportion of subjects will be at least 90% at 24 months (OPC used in the CHAMPION trial). Plotting and analysis of safety endpoints will also be displayed using Kaplan-Meier methods.
 
All safety analyses will be performed on the safety population.
 
Primary Effectiveness Endpoint
 
The primary effectiveness evaluation will compare the annualized HF hospitalization rate at 1 year compared to the HF hospitalization rate in the year prior to enrollment.

This confidential document is the property of Abbott and shall not be reproduced, distributed, disclosed or used without the express written consent of Abbott

Clinical Investigation Plan

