12.6.1. Primary Safety Endpoints

The primary safety analyses will be based on the following objective performance criteria: a) the lower limit of the two-sided 95% confidence interval on the freedom from device / system-related complication rate at 24 months is greater than 80% and b) the lower limit of the two-sided 95% confidence interval on the freedom from pressure sensor failure rate at 24 months is greater than 90%. These primary safety endpoints will be tested hierarchically in order to control for multiplicity. First, the freedom from device / system-related complication rate will be tested. If the result is statistically significant (i.e., $p < 0.050$), then the freedom from pressure sensor failure rate will also be tested for significance (i.e., $p < 0.050$). The study will be judged to have provided positive safety results if both tests of the primary safety analysis endpoints are statistically significant (i.e., $p < 0.050$).

Mathematically stated, the primary safety hypotheses are:

a) $H_0: P_{(\text{Freedom from device / system-related complications at 24 months})} \leq 80\%}$

$H_a: P_{(\text{Freedom from device / system-related complications at 24 months})} > 80\%$

b) $H_0: P_{(\text{Freedom from pressure sensor failure at 24 months})} \leq 90\%$

$H_a: P_{(\text{Freedom from pressure sensor failure at 24 months})} > 90\%$

Plotting and analysis of safety endpoints will also be displayed using Kaplan-Meier methods.

This confidential document is the property of Abbott and shall not be reproduced, distributed, disclosed or used without the express written consent of Abbott

Clinical Investigation Plan

Safety will also be assessed throughout the study by the frequency of Adverse Events (AEs), Adverse Device Effects (ADEs), Serious AEs (SAEs), and Serious Adverse Device Effects (SADEs), and device / system-related complications by relationship to the device via Medical Dictionary for Regulatory Activities (MedDRA) system organ classification. Physical examination, and subject survival data through 24 months will be tabulated across study period assessments.

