13.4. Sub-study Sample Size

The Control group HF hospitalization rate for Part 1 of the CHAMPION study at 1 year was 0.75.

Using an exact one-sample, 2-sided Poisson 95% confidence interval with alpha of 0.05, 114 patients will provide 85% power to show a difference between the estimated Treatment rate of 0.52 and the Control rate of 0.75. Likewise, 130 patients are required to achieve 90% power to show a difference between the estimated Treatment rate of 0.52 and the Control rate of 0.75.

The 2 year attrition rate in CHAMPION was 49.1%, therefore 256 patients $(130/(100\%-49.1\%)) = 256$ is the minimum sample size for this analysis. However, the Independent Committee will identify all patients that are optimally managed and are clinically similar to the Control group in CHAMPION. Therefore, the eligible patients for this sub-cohort and the resultant sample size may be greater.

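### Section 12.2 states women's power for both safety endpoints against 0.90, although the complication criterion is 0.80, and prints the number of women lost (206) as the number completing (about 214)

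*Combined protocol and SAP*

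**What the plan says.** The last paragraph of section 12.2 requires 420 women among the 1200 enrolled and expects "approximately 206 women completing the trial (assuming a 49% attrition rate". It then gives one power statement for both safety endpoints, complications and sensor failure: "206 women will provide greater than 90% power to detect a difference as small as 0.06 from the null proportion rate of 0.90".

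Earlier in the same section the two endpoints are sized separately. Complications need 619 subjects for a difference of 5% "from the null proportion rate of 0.80 (i.e., objective performance criterion of 80" per cent), and sensor failure needs 663 subjects for a difference of 3.5% from 0.90. The complication criterion is 80% elsewhere too. The synopsis hypothesis is that the "complication-free proportion of subjects will be at least 80% at 24 months (OPC used in the CHAMPION trial"), and section 12.6.1 requires a lower confidence limit such that "the freedom from device / system-related complication rate at 24 months is greater than 80" per cent. Sections 13.2, 13.5.1 and 13.9.1 use 80% for the sub-study.

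On attrition, section 12.2 states "The 2 year attrition rate in CHAMPION was 49.1% (228/550"), and section 13.4 uses the rate as the share lost: "The 2 year attrition rate in CHAMPION was 49.1%, therefore 256 patients", obtained by dividing 130 by 100% minus 49.1%.

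**The concern.** There are two slips in one paragraph.

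- **The null.** Two endpoints with different performance criteria share one null, 0.90. A reader takes the sentence to mean over 90% power in women for a 6-point margin on each endpoint. For complications, 0.90 is not a threshold that the plan tests, so the sentence says nothing about power at that endpoint's own criterion.
- **The count.** 206 is what attrition removes from 420, not what it leaves.

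This is the plan's only power figure for safety in women, a group for which it sets an enrolment minimum. The stakes are limited. The planned analyses by sex (sections 10.2.5 and 12.7.2) cover effectiveness only, section 12.6.1 has no safety test in women, and the total of 1200 is driven by 619 and 663.

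**Working it through.** **Inputs from section 12.2:** 420 women; 49% attrition (49.1% where the source rate is given); an exact one-sample binomial test, two-sided 0.05; nulls of 0.80 for complications and 0.90 for sensor failure; a difference of 0.06 for women.

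**Method.** Let k be the smallest count with P(X ≥ k | n, p0) ≤ 0.025, which is the same as the exact 95% lower limit lying above p0. Power is P(X ≥ k | n, p1).

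**1. Reproduce the plan's main figures.** n = 619, 0.85 against 0.80: 90.4%. n = 663, 0.935 against 0.90: 90.5%. Each is the smallest n that reaches 90%, so this is the plan's method.

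**2. Reproduce the women's statement as written.** n = 206, 0.96 against 0.90: k = 194, power 92.8%. The claim of more than 90% holds against 0.90.

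**3. Count of completing women.**

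- Lost: 420 × 0.49 = 205.8, about 206.
- Completing: 420 × 0.51 = 214.2, about 214.
- By the method of section 13.4: 420 × (1 − 0.491) = 213.8, about 214.
- Section 12.2 prints 228/550 beside 49.1%, but 228/550 = 41.5%. If that fraction is the right figure, 420 × (1 − 228/550) = 245.9, about 246.

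**4. Power of each endpoint at its own criterion.**

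| Women | Sensor failure, 0.96 vs 0.90 | Complications, 0.86 vs 0.80 | Complications, 0.89 vs 0.80 | Complications: difference with 90% power |
|---|---|---|---|---|
| 206 | 92.8% (k = 194) | 56.2% (k = 177) | 93.2% | 0.086 |
| 213 | 91.2% (k = 201) | 56.3% (k = 183) | 93.5% | 0.085 |
| 214 | 91.0% (k = 202) | 62.7% (k = 183) | 95.5% | 0.082 |
| 246 | 96.0% (k = 231) | 65.4% (k = 210) | 96.9% | 0.079 |
| 420 | 99.8% (k = 391) | 88.8% (k = 353) | 99.9% | 0.061 |

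Exact power moves in steps, which explains why 213 and 214 differ visibly for complications and why 214 gives slightly less than 206 for sensor failure. For 0.86 against 0.80, power first reaches 90% at 416 women, dips below it again (88.8% at 420), and stays at or above it from 439.

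**5. Other versions of the test.** For 0.86 against 0.80, the normal approximation gives 58.8% (206 women) and 60.7% (214). A one-sided 0.05 exact test gives 70.9% and 69.8%. None reaches 90%.

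**The case against.** The best defence is that 0.90 serves as a common, stricter benchmark. A result that clears 0.90 also clears 0.80, and if true freedom from complications is 0.96, power against 0.80 is above 99.9% at 206 or 214 women. On that reading the sentence is true and cautious, and the 56% to 63% figures arise only by moving the 0.06 difference to 0.80, an alternative of 0.86 that the plan never states. The arithmetic is correct, and the plan gives no expected complication rate that would rule 0.96 out. But the plan nowhere says that a common benchmark was intended. It expresses power as a difference from each endpoint's criterion, and it uses 0.80 for complications earlier in the same section.

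Three further points stand in part:

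- The count error is harmless to the sensor-failure claim, since power exceeds 90% at either number.
- Completers are not the defined analysis set. Section 12.1 takes the safety population regardless of study completion. Using completers follows the plan's own sizing convention, but even all 420 women give 88.8% for 0.86 against 0.80.
- Because of the steps in exact power, the complication figures should not be read to the last digit. A detectable difference of about 0.08 to 0.09 is the fair summary.

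**Conclusion.** Both slips are real, and both are minor. The stated power is right for sensor failure (92.8% at 206 women, 91.0% at 214). It does not describe complications at their own criterion, where a difference of 0.06 has 56.2% power at 206 and 62.7% at 214, and 90% power needs about 0.086 or 0.082. The number completing at 49% attrition is about 214; 206 is the number lost.

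This rests on the exact two-sided 0.05 test, which reproduces the plan's 619 and 663, and on reading 49% as the share lost, as section 13.4 does. If 228/550 is the correct attrition fraction, about 246 women complete and the conclusion is the same: 96.0% for sensor failure, 65.4% for complications. No test, success criterion or total sample size is affected.

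**What to change.** First settle the number of completing women: about 214 at 49% attrition, or about 246 if 228/550 is the right figure. Then replace the single power sentence by two, each with its own criterion. With 214 women:

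> About 214 women are expected to complete (420 × 0.51). Sensor failure: 214 women give about 91% power for a true failure-free proportion of 0.96 against the criterion of 0.90. Complications: 214 women give about 95.5% power for a true complication-free proportion of 0.89 against the criterion of 0.80. Power of 90% is reached at a difference of about 0.08 to 0.09, and a difference of 0.06 has about 63% power.

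The difference of 0.09 is a choice made here for illustration; the sponsor may prefer another.

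- With 246 women: about 96% for sensor failure; for complications about 97% for 0.09, about 65% for 0.06, and 90% at about 0.079.
- If 206 is kept for another stated reason: about 93% for sensor failure; for complications about 93% for 0.09, about 56% for 0.06, and 90% at about 0.086.

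The cost is one corrected number and one sentence split in two. The only visible change is a larger stated detectable difference for complications in women.
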